9.2.1.1. Suspected Unexpected Serious Adverse Reactions

Suspected unexpected serious adverse reactions (SUSARs) are serious events that are not listed in the IB and that the investigator identifies as related to investigational product or procedure. United States 21 CFR 312.32 and European Union Clinical Trial Directive 2001/20/EC and the associated detailed guidances or national regulatory requirements in participating countries require the reporting of SUSARs. Lilly has procedures that will be followed for the identification, recording, and expedited reporting of SUSARs that are consistent with global regulations and the associated detailed guidances.

9.2.2. Complaint Handling

Lilly collects product complaints on investigational products and drug delivery systems used in clinical studies in order to ensure the safety of subjects, monitor quality, and to facilitate process and product improvements.

Subjects will be instructed to contact the investigator as soon as possible if he or she has a complaint or problem with the investigational product so that the situation can be assessed.

9.3. Treatment of Overdose

For this study, any dose of investigational product greater than twice participant's assigned daily dose within a 24-hour time period will be considered an overdose.

In the event of an overdose, the investigator or treating physician should use supportive therapy as necessary and contact the Clinical Research Physician (or designee) immediately.

Decisions regarding dose interruptions or modifications will be made by the investigator in consultation with the CRP based on the clinical evaluation of the participant.

9.4. Safety

9.4.1. *Electrocardiograms*

For each subject, 12-lead digital ECGs will be collected as triplicates according to the Schedule of Activities (Section 2). Subjects must be supine for approximately 10 minutes prior to ECG collection and remain supine but awake during ECG collection.

Consecutive replicate ECGs will be obtained at approximately 1-minute intervals.

Electrocardiograms may be obtained at additional times, when deemed clinically necessary. Collection of more ECGs (more replicates) than expected at a particular time point is allowed when needed to ensure high-quality records.

Electrocardiograms will initially be interpreted by a qualified healthcare provider (the investigator or qualified designee) at the site as soon after the time of ECG collection as possible, and ideally while the subject is still present to determine whether the subject meets entry criteria at the relevant visit(s) and for immediate subject management, should any clinically relevant findings be identified.

Any clinically significant findings from ECGs that result in a diagnosis and that occur after the subject receives the first dose of the investigational treatment should be reported to Lilly or its designee as an AE via eCRF.

If a clinically significant quantitative or qualitative change from baseline is identified after enrollment, the investigator will assess the subject for symptoms (e.g., palpitations, near syncope, syncope) to determine whether the subject can continue in the study. The investigator or qualified designee is responsible for determining if any change in subject management is needed and must document his/her review of the ECG printed at the time of evaluation from at least 1 of the replicate ECGs from each time point.

All digital ECGs will be electronically transmitted to a designated central ECG laboratory. A cardiologist at the central ECG laboratory will then conduct a full over-read on 1 of the replicates (including all intervals). A report based on data from this over-read will be issued to the investigative site. For each set of replicates, the cardiologist will determine the RR and QT intervals, QRS duration, and pulse rate on the ECGs that were not fully over-read. These data are not routinely reported back to the investigative site. However, any clinically significant finding that was not present on the fully over-read ECG will be reported to the investigator and to Lilly. All data from the over-reads will be placed in the Lilly database for analytical and study report purposes.

When there are differences in ECG interpretation between the investigator (or qualified designee) and the cardiologist at the central ECG laboratory, the investigator's (or qualified designee's) interpretation will be used for study entry and immediate subject management.

Interpretations from the cardiologist at the central ECG laboratory will be used for data analysis and report writing purposes.

The investigator (or qualified designee) must document his/her review of 1 of the replicate ECGs printed at the time of collection, the final over-read ECG report issued by the central ECG laboratory, and any alert reports.

9.4.2. Vital Signs

Vital signs including pulse rate, orthostatic BP, temperature, and weight will be measured as detailed in the Schedule of Activities (Section 2).

Orthostatic Blood Pressure Monitoring: For orthostatic BP monitoring, subjects will have 3 BP/pulse rate measurements taken in the seated position approximately 1 minute apart followed by 1 BP/pulse rate measurement taken in the standing position. For orthostatic BP monitoring, subjects should be seated for at least 5 minutes and stand for at least 3 minutes prior to taking the respective measurements. If the subject feels unable to stand, vital signs only in the seated position will be recorded.

Orthostatic BP/pulse rate will be measured as part of the vital sign assessments at every visit. At Visit 2, Visit 3, Visit 8, Visit 11, and Visit 801, these measurements will be collected at time 0 of the in-clinic BP/pulse rate monitoring. Unscheduled orthostatic vital signs should be assessed, if possible, during any AE of dizziness or posture-induced symptoms. Additional vital signs may be measured during each study period if warranted and agreed upon between the sponsor and investigator. (Table HBEH.3)

In-clinic Blood Pressure and Pulse Rate Monitoring: In-clinic BP and pulse rate monitoring will be done at Visit 2, Visit 3, Visit 8, Visit 11, and Visit 801. The BP and pulse rate will be measured at time 0 and every 60 minutes thereafter. The initial measurement, at time 0 of the in-clinic BP and pulse rate monitoring, will be done as an orthostatic BP/pulse rate (refer to Orthostatic Blood Pressure Monitoring above), and subsequent BP and pulse rate measurements will be taken in the seated position only. Time 0 at Visit 3, Visit 8 and Visit 11 will occur just prior to study drug dosing. At Visit 3, drug dosing should be initiated immediately following confirmation that subject met inclusion criteria [6]. At Visit 2, Visit 8, and Visit 11, in-clinic BP and pulse rate will be monitored for up to 6 hours, At Visit 3, for up to 8 hours and at Visit 801 for up to 2 hours (Table HBEH.4).

Home Blood Pressure Monitoring: Home BP measurements will be collected in this study. Blood pressure measurements should be taken twice daily in the seated position using the HBPM equipment provided by Lilly. The subject should be given the HBPM device at Visit 2. Home BP measurements should be conducted for a minimum of 7 days between Visits 2 and 3, for 3 weeks between Visits 3 and 6, and a minimum of 7 days between Visits 10 and 11, and Visits 11 and 801. Home BP should be taken twice in the morning (approximately 1 minute apart) (e.g., 8 AM) immediately following study medication dosing and twice in the evening, approximately 12 hours later (approximately 1 minute apart) (e.g., 8 PM).

All HBPM data will be electronically transmitted to a designated HBPM data processing vendor.

9.4.3. Laboratory Tests

For each subject, laboratory tests detailed in ([Appendix 2](#)) should be conducted according to the Schedule of Activities (Section 2).

With the exception of laboratory test results that may unblind the study, Lilly or its designee will provide the investigator with the results of laboratory tests analyzed by a central vendor, if a central vendor is used for the clinical trial.

Any clinically significant findings from laboratory tests that result in a diagnosis and that occur after the subject receives the first dose of investigational product should be reported to Lilly or its designee as an AE via eCRF.

9.4.4. Columbia-Suicide Severity Rating Scale – Children’s Version

Consistent with Food and Drug Administration (FDA) regulatory guidance (FDA 2012), any occurrence of suicide-related thoughts and behaviors will be assessed as indicated in the Study Schedule (Section 2). The C-SSRS is a scale that captures the occurrence, severity, and frequency of suicide-related thoughts and behaviors during the corresponding assessment period. The scale includes suggested questions to elicit the type of information needed to determine if a suicide-related thought or behavior occurred.

The C-SSRS is available in an adult’s and a children’s version. There is no version of the C-SSRS designed for use in a cognitively impaired population such as subjects with PD dementia; therefore, the children’s version will be used. Terms captured by the use of the C-SSRS children’s version can be mapped to Columbia Classification Algorithm for Suicide Assessment (Posner et al. 2007), to facilitate future pooling of data.

The first time the scale is assessed in this study, the C-SSRS “Baseline” version will be used, and the findings will constitute the baseline assessment. The C-SSRS “Since Last Visit” scale will be used for all subsequent assessments.

The C-SSRS will be assessed after the cognitive and functional assessments. Responses from subject will be considered when assessing the scale. If a suicide-related thought or behavior is identified at any time during the study, a thorough evaluation will be performed by a study physician, and appropriate medical care will be provided.

If, based on assessment of the C-SSRS, it is determined that suicide-related behaviors have occurred, then the Lilly Self-Harm Follow-Up form will be used to collect additional information to allow for a more complete assessment of these behaviors.

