Interim Analysis: Safety interim analyses will be conducted on the number of subjects on each treatment who met the potentially clinically significant vital signs criteria (Table HBEH.3) at 3 *consecutive* time points at Visit 3 (Day 1 stopping rules). This will be done after 50, 100, and 150 subjects have completed Visit 3. CCI

Those already on 75-mg dose and passed the Day 1 stopping rules will remain on 75 mg. In the event of an unacceptable rate of subjects meeting Day 1 stopping rules at other doses, adjustments to doses may be made for subsequently randomized subjects at the discretion of the Internal Assessment Committee (IAC). Additional efficacy analyses may be conducted at the time of these safety interim analyses. A safety and efficacy interim analysis will be conducted when 170 randomized subjects have completed Visit 11 (Week 12) assessments and may also be conducted at other timepoints prior to study completion. All potential efficacy analyses may be used for internal decision making, but are not planned to stop the study.

2. Schedule of Activities

Table HBEH.1. Schedule of Activities for Protocol I7S-MC-HBEH

Procedure ^a	Screening	Pretreatment	Double-Blind Treatment									Follow-up		Unscheduled Visit	ET/DC Visit ^{d,t}
			7 days	14 days	21 days	28 days	42 days	56 days	70 days	84 days	2 days after V11 ^u	14 days from V11 or ET/DC			
Study Day	Min 7 days; max 14 days prior to V2	Min 11 days; max 17 days prior to V3													
Tolerance Interval for Visit (Days)		Baseline Visit	Randomization	±1	±1	±1	±1	±3	±3	±3	±3	+1	±3		
eCRF Visit No.:	V1^{b,d}	V2^{b,d}	V3^b	V4^d	V5	V6	V7	V8^{b,d}	V9	V10	V11^{b,d}	V11^u	V801	V997^c	
Informed Consent(s) Signed (before procedures/tests)	X														
Register subject in IWRS - Subject number assigned	X														
Complete IWRS	X	X	X	X	X	X	X	X	X	X	X		X	X	X
Demographics	X														
Prior/concomitant treatment	X	X	X	X	X	X	X	X	X	X	X		X	X	X
Inclusion/exclusion criteria	X	X	X												
Modified Hoehn and Yahr Scale	X														
Medical History	X														
Physical Examination ^e	X							X			X		X		X
Height		X													
Weight		X						X			X				X
Orthostatic BP/pulse rate ^f	X	X	X	X	X	X	X	X	X	X	X		X	X	X
In-clinic BP/Pulse rate monitoring ^g		X	X					X			X		X		

Procedure ^a	Screening	Pretreatment	Double-Blind Treatment										Follow-up		Unscheduled Visit	ET/DC Visit ^{d,t}
				7 days	14 days	21 days	28 days	42 days	56 days	70 days	84 days	2 days after V11 ^u	14 days from V11 or ET/DC			

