- l An iPad® configured with the Lilly Trial application (Lilly Trial app) will be provided to the subjects at Visit 2 (if available). Subjects should complete assessments from 2 weeks prior to dosing (starting the day following Visit 2), throughout the dosing period, and for 2 weeks after the conclusion of the treatment period (until Visit 801). This assessment should be done up to twice daily. Subjects will self-select for this optional component of the protocol at Visit 1. Subjects can decide to opt out at any time during the study. In case of opt-out or ET, the subject should return the iPad to the site at the visit following the subject opt-out or at the ET/DC visit. For subjects who complete the Lilly trial application assessments throughout the study, the iPad should be returned at Visit 801. Refer to the Operations Manual for details about Opt-in and Opt-out process.
- m The actigraphy device (if available) should be worn on the wrist, similar to a watch, beginning at Visit 2, for 3 separate 2-week periods of time: Visit 2 to Visit 3, Visit 8 to Visit 9, and Visit 11 to Visit 801. The site will provide the device to the subjects at Visits 2, 8, and 11.
- n Following 14 days of wearing the device, the subject should bring the device back to the site at the next scheduled visit (Visit 3, Visit 9, or Visit 801).

- o CDR-CCB: At least 2 training sessions are required at Visit 1. At each visit, the CDR-CCB should be assessed after the study drug has been dosed. At Visit 4, Visit 5, Visit 6, Visit 7, Visit 9, and Visit 10, if a subject has not taken the study drug prior to the study visit, the subject must take study drug at the site prior to the CDR-CCB.

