5.1.3.1. Orthostatic BP/Pulse Rate Measurements

Prior to dosing, orthostatic BP/pulse rate measurements will be collected at time 0 of the in-clinic BP/pulse rate monitoring. Subjects will have 3 BP/pulse rate measurements taken in the seated position approximately 1 minute apart followed by 1 BP/pulse rate measurement taken in the standing position. Subjects should be seated for at least 5 minutes and stand for at least 3 minutes prior to taking the respective measurements. If the subject feels unable to stand, vital signs only in the seated position will be recorded.

The mean should be calculated from the 3 initial in-clinic BP/pulse rate measurements taken in the seated position, and must meet inclusion criteria [6] in order to proceed with dosing (Table HBEH.4). At Visit 3, subjects not fulfilling inclusion criteria [6] at their time 0 BP/pulse rate measurements can have their BP/pulse rate re-evaluated within 3 days. If inclusion criteria [6] is subsequently met (within 3 days of Visit 3), subject may proceed with dosing. If inclusion criteria [6] is subsequently not met (within 3 days of Visit 3), the subject must be discontinued. Subjects who continue to meet entry criteria will be randomized to LY3154207 (10, 30, or 75 mg QD) or placebo immediately following confirmation that subject meets inclusion criteria [6]. Subjects should be dosed immediately after randomization.

The time 0 mean BP and pulse rate will be used for the baseline measurement to assess the change threshold for the development of potentially clinically significant BP/pulse rate (Table HBEH.3).

After time 0, in-clinic BP and pulse rate measurements will be taken every 60 minutes in the seated position only for up to 8 hours. Subjects who meet potentially clinically significant BP/pulse rate measurement (Table HBEH.3) at 3 consecutive timepoints (Day 1 stopping rules) should be discontinued from the study.

Table HBEH.3. Potentially Clinically Significant Vital Sign Criteria

	Low^a	High^a
Systolic BP (mm Hg)	≤90 AND ≥20 decrease	≥180 AND ≥20 increase
Diastolic BP (mm Hg)	≤50 AND ≥15 decrease	≥105 AND ≥15 increase
Pulse Rate (bpm)	≤50 AND ≥15 decrease	≥120 AND ≥15 increase
Abbreviations: BP = blood pressure, bpm = beats per minute, mm Hg = millimeters of mercury		

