5.1.3.3. Home Blood Pressure Monitoring

Home BP measurements should be conducted for a minimum of 7 days between Visit 2 and Visit 3, for approximately 3 weeks between Visit 3 and Visit 6, and for a minimum of 7 days between Visit 10 and Visit 11, and Visit 11 and Visit 801. Home BP should be measured twice in the morning (approximately 1 minute apart) (e.g., 8 AM) immediately following study medication dosing and twice in the evening, approximately 12 hours later (approximately 1 minute apart) (e.g., 8 PM).

5.1.3.4. Visit 4 to Visit 11

Visits will occur at weekly intervals (7 days \pm 1 day) for Visit 4 through Visit 7, and will occur at biweekly intervals (14 days \pm 3 days) for Visit 8 through Visit 11.

Study drug is to be administered at the clinic on the morning of Visit 8 and Visit 11 following the Time 0 in-clinic BP/pulse rate measurements.

In-clinic BP/pulse rate monitoring at Visit 8 and Visit 11 will be conducted as described in Section 5.1.2.

At each visit, the CDR-CCB should be assessed after the study drug has been administered. At Visit 4, Visit 5, Visit 6, Visit 7, Visit 9, and Visit 10, if a subject has not taken study drug prior to the study visit, the subject must take study drug at the site prior to the CDR-CCB assessment.

MoCA, ADAS-Cog13, MDS-UPDRS [Part III], and D-KEFS will be performed according to the Study Schedule.

Caregiver's inputs will be needed at Visit 4, Visit 8, Visit 11, or ET/ DC for the PDAQ-15, Alzheimer's Disease Cooperative Study – Clinician Global Impression of Change (ADCS-CGIC), MDS-UPDRS, NPI, ESS, GDS-S, and/or QUIP scales. Caregiver's input, separate from the subject, will be needed at Visit 11, Visit 111 and Visit 801 for the PWC-20 early termination.

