7.2. Method of Treatment Assignment

Subjects who meet all criteria for enrollment will be randomized to double-blind treatment at Visit 3. Subjects will be randomized in a blinded fashion to the 4 treatment arms (Placebo; LY3154207 10 mg; LY3154207 30 mg; LY3154207 75 mg [or 50 mg based on interim analysis – refer to Section 10.3.7]) at 1:1:1:1 ratio. Randomization will use a minimization procedure in order to balance for investigator site and the current use of AChEIs (Yes, No) using an interactive web-response system (IWRS).

The IWRS will be used to assign blister packs containing double-blind investigational product to each subject. One blister pack will be dispensed for each week of dosing, for example, for 14-day study intervals, 2 blister packs will be dispensed at each visit. Site personnel will confirm that they have located the correct blister packs by entering a confirmation number found on the blister packs into the IWRS.

Selection and Timing of Doses

The doses should be administered at approximately the same time each day in the morning. At Visit 3, Visit 8, and Visit 11, the dose will be administered at the clinic. The actual date and time of the dose administrations on the day of Visit 3, Visit 4, Visit 5, Visit 8, Visit 11, and ET/DC visit will be recorded in the subject's eCRF.

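### As the protocol's ordering rules read together, the Visit 3 C-SSRS falls after randomization and the first dose, so the Visit 3 check of exclusion [34] rests on the Visit 2 form

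*Protocol*

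**What the plan says.** **Eligibility at Visit 3.** Protocol Section 5.1.3.1: "Subjects who continue to meet entry criteria will be randomized to LY3154207 (10, 30, or 75 mg QD) or placebo immediately following confirmation" that inclusion [6] is met. Section 7.2: "Subjects who meet all criteria for enrollment will be randomized to double-blind treatment at Visit 3". The Schedule of Activities row "Inclusion/exclusion criteria" is marked at Visits 1, 2 and 3.

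**Dosing.** Section 5.1.3.1: "Subjects should be dosed immediately after randomization". A subject who fails [6] at Visit 3 "can have their BP/pulse rate re-evaluated within 3 days".

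**The criterion.** Exclusion [34] (Section 6.2) applies to a subject who answers yes to C-SSRS ideation question 4 or 5, or to any suicidal behavior item, where the event fell in the past month.

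**The C-SSRS.** The Baseline version is given at Visit 1 and the Since Last Visit version afterwards, including at Visit 3 (Schedule row; footnotes q and r). Section 9.4.4 fixes its place in the visit: "The C-SSRS will be assessed after the cognitive and functional assessments". Section 5.1.1.1.7 gives the same order in its screening description.

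**The CDR-CCB.** Footnote o: "At each visit, the CDR-CCB should be assessed after the study drug has been dosed". Section 5.1.3.4, headed Visit 4 to Visit 11, repeats it: "At each visit, the CDR-CCB should be assessed after the study drug has been administered".

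**Order in general.** Footnote a refers the order of procedures to the Operations Manual.

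**The concern.** A form whose answers define an exclusion criterion, and which is already scheduled at the randomization visit, should inform the decision to randomize. Under the ordering rules it seems to come too late to do so. A subject with new suicidal ideation or behavior since Visit 2 would then be randomized and given study drug before the form is completed. Section 8.1.3 would afterwards treat that subject as inadvertently enrolled: treatment should stop unless the sponsor's clinical research physician documents approval to continue. With the form done first, the same subject would be neither randomized nor dosed. What is at stake is eligibility and subject safety; the treatment comparison is essentially untouched.

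**Working it through.** No sample size or power figure is involved. The check chains the ordering rules and then does simple day arithmetic.

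**Order at Visit 3**

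1. Time 0 vital signs, and inclusion [6] confirmed (5.1.3.1).
2. Randomization of subjects who still meet entry criteria (5.1.3.1, 7.2).
3. First dose, at once (5.1.3.1).
4. CDR-CCB, after the dose (footnote o). It is the only cognitive or functional scale marked at Visit 3.
5. C-SSRS, after the CDR-CCB (9.4.4).

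The C-SSRS is fifth and the decision it bears on is second. No protocol sentence exempts Visit 3 from either ordering rule or places its C-SSRS before randomization.

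**Is the Visit 3 CDR-CCB really post-dose?** Two other places are consistent with footnote o, though both are inferences.

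- Baseline is by default the last value before treatment (Protocol 10.3.1, SAP 6.2), yet Protocol 5.1.1.1.2 and SAP 6.5 name Visit 2 as the CDR-CCB or CoA baseline. A pre-dose Visit 3 session would have been the default baseline.
- The example code in SAP 6.12.1 models nine CoA values and gives the first one a treatment effect. Visits 4 to 11 are 8 visits; adding Visit 3 gives 9. The code does not label the visits. Adding Visit 801 would also give 9, but less naturally for an analysis to Week 12. The SAP text lists only Weeks 1 to 12.

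**Does [34] apply at randomization?** Section 6.2 excludes subjects from enrollment, and Appendix 1 defines enrolling as assigning a subject to treatment. So [34] governs at randomization. Nothing says that a same-day C-SSRS is needed to check it.

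**Age of the newest C-SSRS at randomization**

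- Visit 2 to Visit 3 gap: 11 to 17 days (Section 5.1).
- Outer limit: 17 + 3 = 20 days. This needs a failed blood pressure or pulse check and no C-SSRS completed at that first attendance.
- Forms available for the check: 2 as ordered (Visits 1 and 2); 3 if the Visit 3 form comes first.

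**Exposure before the Visit 3 form**

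- Normally 1 dose, within a visit of about 8 hours that has hourly blood pressure and pulse readings.
- Outer limit: footnote b allows clinical assessments to move to the next day in exceptional circumstances, and the C-SSRS is not among the procedures that must be done on the first day. If it counts as a clinical assessment and does move, exposure is 1 to 2 doses.

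Both outer limits rest on several conditions holding at once and are not the expected size.

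**The case against.** The strongest case against acting has four parts.

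**The order may already be settled elsewhere.** Footnote a defers to the Operations Manual, and no single protocol sentence puts the C-SSRS after the first dose. This stands: the order used at sites is unknown. But a manual that put the form first would depart from footnote o read with 9.4.4, so the protocol text would still benefit from a clarifying sentence.

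**Some links are soft.** Footnote o is worded as a recommendation and cannot apply at Visits 1, 2 and 801, where no drug is given. Section 5.1.3.4 repeats the rule only for Visits 4 to 11, and 5.1.1.1.7 belongs to screening. These limits stand, although footnote o speaks of each visit and its row includes Visit 3.

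**Nothing is strictly contradictory.** A reader might infer that the protocol requires something at Visit 3 that its own order makes impossible. The documents do not support that. Exclusion [34] can be checked on the Visit 1 and Visit 2 answers, and Section 6.1 names only [6] as having to be met at additional visits. That note concerns inclusion criteria, so it does not switch off [34], but neither does any text demand a fresh C-SSRS for it.

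**The consequence is small and handled.** A reader might also infer that events between Visits 2 and 3 go unassessed. They do not: the Since Last Visit form looks back over the whole gap, a positive answer leads to a physician evaluation, and 8.1.3 directs what follows. This stands and limits the harm to late detection.

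**Conclusion.** The point holds as a sequencing weakness. As the text reads, the Visit 3 C-SSRS follows randomization and the first dose, and the Visit 3 check of [34] uses a form normally 11 to 17 days old. For a subject with a new [34] event in that gap, the cost is an avoidable randomization and about one monitored dose, followed by 8.1.3.

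The documents give no incidence, so the number of such subjects is unknown; it is probably very small. Efficacy estimates are essentially unaffected. Such a subject could meet the Evaluable Patient Population definition, with one dose, a Visit 2 baseline and a post-dose CDR-CCB, but a few cases would hardly move the estimates. The planned C-SSRS output is only a listing (Protocol 10.3.4.2).

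The conclusion assumes that footnote o applies at Visit 3 and that the Operations Manual does not set a different order. It says nothing about what sites did. The change is worth making because the form is already scheduled and only its position needs to move.

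**What to change.** Add one sentence to Protocol Section 9.4.4: at Visit 3 only, the C-SSRS is completed and reviewed against exclusion [34] before randomization, with the order at all other visits unchanged. Align the Operations Manual for that visit. If the manual already does this, the protocol sentence alone is enough.

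No assessment is added. There are two small downsides.

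- Inclusion [16] does not require the caregiver at Visit 3, so the study partner may have to be reached by telephone before randomization. Section 5.1.1.1.7 already allows telephone contact for this scale.
- At Visit 3 the C-SSRS would come before the CDR-CCB. That session is not the Week 12 endpoint, but the nine-value example code suggests that it is one of the repeated measures in the primary model. The order would be the same in all arms, and the form would be completed before assignment, so no bias between arms is expected.
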